**Impact of The Real Cost Vaping Prevention Advertisements on
Adolescents**

Hypotheses and Analytic Plan

NCT #04836455

Version Date: 4/23/2021

Hypotheses

The goal of this study is to determine whether exposure to vaping prevention advertisements reduce susceptibility to vaping. The **primary hypothesis** is that participants who view *The Real Cost* vaping prevention advertisements will have lower susceptibility to vaping compared to those who view neutral vaping control ads at 3 week follow-up.

The investigators also aim to examine the impact of *The Real Cost* vaping prevention ads on a series of other vaping-related outcomes. **Additional hypotheses** are that, compared to exposure to neutral vaping ads, participants exposed to *The Real Cost* vaping prevention ads will report the following at 3-week follow-up:

- Lower susceptibility to vaping
- Higher health harm risk beliefs about vaping
- Higher addiction risk beliefs about vaping
- More negative attitudes toward vaping
- Less vaping
- Higher attention (assessed only at 2-week follow-up)
- Higher negative affect (assessed only at 2-week follow-up)
- Higher cognitive elaboration
- More social interactions

The investigators will also explore the effects of *The Real Cost* vaping prevention ads on cigarette smoking-related outcomes, compared to exposure to neutral vaping ads. There are **not have directional hypotheses** for the following outcomes:

- Susceptibility to smoking cigarettes
- Health harm risk beliefs about smoking cigarettes
- Addiction risk beliefs about smoking cigarettes
- Attitudes towards smoking cigarettes
- Cigarette smoking behavior

Finally, the investigators will explore whether health harms vaping prevention ads out-perform addiction *The Real Cost* ads. We have labeled this an exploratory activity because the study is powered to compare these ads to control ads but not to one another.

Primary analyses

The investigators will use a critical alpha of 0.05 in all statistical tests. Analyses of the primary and secondary outcomes will include all randomized participants according to the trial arm they were randomized to receive (i.e., intent-to-treat). The investigators will use multiple imputation to handle any missing data on predictors and full information maximum likelihood to handle any missing data on outcomes.

The investigators will report univariate and bivariate descriptive statistics for the primary and secondary outcomes.

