For significance testing of the primary hypotheses, the investigators will compare those in *The Real Cost* trial arms (combined) to the control arm. The investigators will use latent curve models so that the investigators can model change in repeated measures over time. After establishing a linear growth trajectory for each latent construct with the intercept coded to be at the last time point, the investigators will regress the latent intercept and slope factors for each outcome on an indicator of random assignment to *The Real Cost* trial arms or to the control arm.

A significant effect on the intercept will indicate a main effect of treatment assignment on the mean level of each outcome at the last time point. A significant effect on the slope, if positive, will indicate that repeated viewing of the ads led to an increase in the difference across trial arms. If negative, it will indicate that the treatment effect diminished over time. As a secondary analysis, the investigators will examine whether there were significant differences in growth factor means as a function of assignment to the *The Real Cost* ad trial arms.

The investigators will also conduct the above analyses comparing those in the *The Real Cost* health harms trial arm to those in the *The Real Cost* addiction trial arm to explore whether there are differences across those trial arms.

The investigators will use a separate model for each of the study outcomes. To account for multiple comparisons, the investigators will use a Benjamini-Hochberg correction to maintain a 5% false detection rate.

Finally, the investigators will conduct exploratory moderation analyses on the primary outcome to examine whether the following variables moderate the impact of *The Real Cost* trial arms (compared to the control arm) on susceptibility to vaping: gender, age, race, Hispanic ethnicity, sexual orientation, parent's education, current vaper (vs. non-current vaper), and tobacco user in the household.

Sample size and power

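### One sign rule for the slope effect is applied to outcomes expected to move in opposite directions, so under any single arm coding it gives the wrong verdict for one group; with Real Cost coded 1, a growing benefit on susceptibility is read as fading

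*SAP*

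**What the plan says.** The SAP (Primary analyses) fits a linear latent curve model to each outcome with the intercept placed at the last visit, and "the investigators will regress the latent intercept and slope factors for each outcome on an indicator of random assignment to" Real Cost or control. The arm coded 1 is not named. The intercept effect is read as a "main effect of treatment assignment on the mean level of each outcome at the last time point".

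The slope effect gets one rule for all outcomes. For a positive effect: "A significant effect on the slope, if positive, will indicate that repeated viewing of the ads led to an increase in the difference" between arms. For a negative one: "If negative, it will indicate that the treatment effect diminished over time".

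The hypotheses point in both directions. Real Cost participants "will have lower susceptibility to vaping compared to those who view neutral vaping control ads at 3 week follow-up", and less vaping is expected. For other outcomes the expected effect is upward, for example "Higher health harm risk beliefs about vaping"; the same holds for addiction risk beliefs, attention, negative affect, cognitive elaboration and social interactions. Five smoking outcomes have no directional hypothesis.

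The Protocol (Measures) scores susceptibility so that a higher value means more susceptible, and most secondary scales so that a higher value means more of the construct. No reverse-scoring is described.

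**The concern.** Whether an arm difference grows or shrinks depends on the sign of the slope effect relative to the sign of the difference itself. A rule that looks at the slope sign alone cannot serve outcomes expected to fall and outcomes expected to rise under the same arm coding.

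At stake is the SAP's only stated reading of whether repeated viewing strengthens or weakens the ads' effect. Followed literally with Real Cost coded 1, it would report a strengthening effect on the primary outcome as fading, and a fading one as strengthening.

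**Working it through.** **Inputs.** From the SAP: linear trajectory, intercept at the last visit, one arm indicator, the sign rule, the hypothesised directions. From the Protocol: the scoring; four visits for most outcomes; three for attention and negative affect, last measured at Visit 3; days vaped and days smoked reported before the ads at Visit 1. Assumed: time scored forward, the usual convention. The documents give no slope values, so every effect size below is also an assumption.

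**Algebra.** Let D(t) be the arm difference (arm coded 1 minus the other) at visit t, and T the last visit:

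D(t) = b_int + b_slope × (t − T), so D(1) = b_int − (T − 1) × b_slope.

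If D does not cross zero, its absolute size grows exactly when b_slope and b_int have the same sign. The statement that positive means growing is therefore right only when b_int > 0.

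**Signs on a simple example.** Control mean 2.0 throughout; benefit of 0.05, 0.10, 0.15, 0.20 over four visits (growing) or the reverse (shrinking); Real Cost = 1:

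| Outcome and true course | b_int | b_slope | SAP label | Correct? |
|---|---|---|---|---|
| Susceptibility, growing benefit | −0.20 | −0.05 | diminished | no |
| Susceptibility, shrinking benefit | −0.05 | +0.05 | increase | no |
| Risk beliefs, growing benefit | +0.20 | +0.05 | increase | yes |
| Risk beliefs, shrinking benefit | +0.05 | −0.05 | diminished | yes |

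With control = 1 all signs flip: susceptibility is then labelled correctly and risk beliefs wrongly. Scoring time backwards also only swaps the group. In all four combinations exactly one group is reversed.

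**Grid.** b_int from −0.50 to 0.50 by 0.05 and b_slope from −0.20 to 0.20 by 0.01, zeros excluded, D(1) and D(T) of the same sign. For T = 4 the SAP label is right in 285 of 285 cells with b_int > 0 and 0 of 285 with b_int < 0; for T = 3, 324 of 324 and 0 of 324. This only confirms the algebra.

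**Outcomes affected.** Nine vaping-related outcomes, less attitudes (score direction not given), leave eight: two expected lower (susceptibility, days vaped) and six expected higher. The rule is reversed for two if Real Cost = 1 and for six if control = 1.

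**Would such slopes be detected?** Take 1000 versus 500 participants, SD 1, ICC 0.7, compound symmetry, known variances and no dropout.

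- Slope: variance = (0.3 / 5) × (1/1000 + 1/500) = 0.06 × 0.003 = 0.00018, SE = 0.0134.
- D(1) and D(4): variance = [0.7 + 0.3 × (1/4 + 1.5²/5)] × 0.003 = 0.91 × 0.003 = 0.00273, SE = 0.052.
- A change from −0.10 to −0.25 is −0.05 per visit: 0.05 / 0.0134 = 3.73, and Φ(3.73 − 1.96) = Φ(1.77) = 0.96.

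With assumed retention of 100/89/78/67% the slope SE is 0.0156 and the slope is significant in about 90% of runs. Significance is two-sided 0.05 before any Benjamini-Hochberg correction.

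**Labels among runs with a significant slope** (200,000 draws, Real Cost = 1, no dropout). The last column applies the first-versus-last-visit comparison proposed below:

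| True difference, first to last visit | SAP rule | First-versus-last comparison |
|---|---|---|
| Susceptibility −0.10 to −0.25 | diminished, 100% | widening, 100% |
| Susceptibility −0.40 to −0.25 | increase, 100% | diminishing, 100% |
| Susceptibility −0.25 to 0 | increase, 100% | diminishing 97.5%, reversing 2.3% |
| Susceptibility −0.04 to −0.10 | diminished, 99.9% | widening 93%, diminishing 7% |
| Risk beliefs +0.10 to +0.25 | increase, 100% | widening, 100% |

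**Days vaped and days smoked.** The Visit 1 report precedes exposure, so the expected D(1) is zero and the estimate there is noise. For a true change from 0 to −0.10, comparing absolute sizes would say diminishing in 15% of significant runs (14% with dropout), whereas the slope sign gives the right direction in 100%. These two outcomes need their own reading.

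**The case against.** Nothing inferential is wrong: every hypothesis concerns level at the 3-week (or 2-week) follow-up, the intercept tests it, and no estimate, p-value or multiplicity decision depends on the slope sentence. That stands, and it caps the severity.

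The SAP can also be read more kindly. Its wording about an increasing difference and a diminishing effect is about size, so a positive slope might mean one in the direction of the intercept effect, or in the favourable direction. Since "The investigators will use a separate model for each of the study outcomes", the arm coding could also differ by outcome. None of this is in the text. The favourable-direction reading has no meaning for the five smoking outcomes. The two-ad comparison ("The investigators will also conduct the above analyses comparing those in the" health harms and addiction arms) inherits the rule without a reference arm.

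The susceptibility example needs Real Cost = 1 and forward time, and the reversed group is identified by assuming effects fall as hypothesised. These conditions are fair. They decide which group is reversed, not whether one is. The simulation adds little on the SAP rule itself, since its labels follow from the assumed signs.

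Finally, one sentence might suffice: same sign as the intercept means widening, opposite sign means narrowing. It works while a clear difference remains at the last visit. If the effect fades fully (−0.25 to 0), the sign of the estimated intercept is a coin toss, and about half of significant runs would be called widening.

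**Conclusion.** The concern holds as a minor error of interpretation. The written rule is wrong, not merely incomplete: under any single arm coding used for all outcomes it gives the opposite verdict for one group. With Real Cost = 1 that group includes the primary outcome. This rests on the rule meaning the sign of the coefficient, on effects in the hypothesised directions and on a difference that does not cross zero; the susceptibility example also takes time as scored forward. The last-visit test of the primary hypothesis and all p-values are unaffected.

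**What to change.** State Real Cost = 1 and control = 0 in every model, and name the arm coded 1 in the health harms versus addiction comparison. Replace the two sentences on the slope with:

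> A significant slope effect is interpreted from the model-implied arm differences at the first and last assessed visits, reported with 95% CIs for every outcome. The difference is described as widening if its absolute size is larger at the last visit than at the first, and as diminishing if it is smaller. If the two differences have opposite signs and both CIs exclude zero, it is described as reversing instead. For days vaped and days smoked, Visit 1 is a pre-exposure baseline with an expected difference of zero; there a significant slope effect is reported as an arm difference that developed after exposure, with its direction given by the sign of the slope (negative = fewer days in the arm coded 1).

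The cost is this wording and one table: 14 outcomes × 2 visits = 28 differences with CIs for Real Cost versus control, and 28 more for the two-ad comparison. No new data, model or test is needed. Because the Protocol describes recruitment as complete, any slope interpretation already reported should be checked against this reading.

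One limit remains. If the difference truly crosses zero during the trial (for example +0.15 to −0.15), the reversing label is reached in 64% of runs (57.6% with dropout) and the rest split between the other two labels; the reported CIs would show this.

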## Measures

At the first session (Visit 1), each participant reported vaping and smoking behaviors in the survey, then viewed ads that corresponded to their trial arm. They completed measures assessing message reactions after viewing each ad, after which they completed measures of susceptibility to vaping and smoking, vaping and smoking beliefs, and demographics. For the subsequent weeks of the trial (Visits 2 and 3), participants completed surveys with measures of susceptibility to vaping and smoking, vaping and smoking beliefs, and vaping and smoking behavior. Then, they viewed the same three ads from their trial arm and completed the message reactions items. At Visit 4, participants completed surveys assessing susceptibility to vaping and smoking, vaping and smoking beliefs, and vaping and smoking behavior (eFigure 1 in the Supplement).

**Primary outcome.** Susceptibility to vaping at Visit 4 was the primary trial outcome. Susceptibility prospectively predicts vaping behavior, including as a scaled score where higher values predict both greater initiation and current use of vapes. We assessed susceptibility with a 3-item susceptibility to vaping scale, similar to other studies. This scale assesses the extent to which adolescents are open to vaping, with a 4-point response scale ranging from “definitely not” (coded as 1) to “definitely yes” (coded as 4) (eTables 2 and 3 in the Supplement). We calculated a susceptibility score by averaging the 3 items, with higher scores representing higher susceptibility (Cronbach’s  $\alpha=.93$ ). Susceptibility was measured *after* ad exposure at Visit 1 to capture immediate ad impact and *before* ad exposure at Visits 2-4 to capture ad impact over time.

**Secondary outcomes.** The survey assessed several secondary outcomes hypothesized to elicit behavior change. Response scales for most secondary outcomes had five points, coded such

that higher scores represented a greater amount of the construct. For multi-item scales, overall scale scores were of the average of the items.

*Message reactions.* A single item assessed attention to the message and a 3-item scale assessed negative affect ( $\alpha=.83$ ). Message reactions were measured immediately following ad exposure. These measures were last assessed at Visit 3 because the ads were not shown at Visit 4.

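### The SAP's rule for reading the slope effect is wrong as written: its sign cannot suit all outcomes, and a slope that includes Visit 1 does not isolate repeated viewing

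*SAP*

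**What the plan says.** The SAP (Primary analyses) plans a separate latent curve model for each outcome: "After establishing a linear growth trajectory for each latent construct with the intercept coded to be at the last time point". Intercept and slope are then regressed on an indicator of random assignment. The SAP does not say which arm is coded 1 or which visits enter the line. A significant slope effect, "if positive, will indicate that repeated viewing of the ads led to an increase in the difference across trial arms". For the other sign: "If negative, it will indicate that the treatment effect diminished over time". On multiplicity, "the investigators will use a Benjamini-Hochberg correction to maintain a 5% false detection rate", without defining the family of tests.

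The protocol (Measures) fixes direction and timing:

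- Susceptibility is a mean of three items, "with higher scores representing higher susceptibility". The SAP (Hypotheses) predicts that it falls under the Real Cost ads, while risk beliefs, cognitive elaboration and social interactions rise.
- Susceptibility was taken after "ad exposure at Visit 1 to capture immediate ad impact", but before that day's ads at Visits 2-4. The other vaping scales follow the same split. The Visit 1 order also puts smoking susceptibility and smoking beliefs after the ads.
- Behavior is different. At Visit 1, "each participant reported vaping and smoking behaviors in the survey, then viewed ads that corresponded to their trial arm". Days vaped was reported before the ads at every visit, over a 7-day recall window.
- For attention and negative affect, "Message reactions were measured immediately following ad exposure", last at Visit 3.

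**The concern.** The rule turns the sign of one coefficient into a causal statement about repeated viewing. That needs two things: a positive coefficient must mean a growing benefit for every outcome, and the visits on the line must differ only in how often the ads have been seen. Neither holds.

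Followed literally, the rule could report a growing benefit on the primary outcome as a fading one. It could report an effect on days vaped that began after the first session and never grew as evidence that repetition widened the gap. It could also miss real growth in susceptibility because of a strong immediate reaction at Visit 1. The Visit 4 effect, which answers the primary hypothesis, is less exposed, but it comes from the same line.

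**Working it through.** **Inputs.** From the documents: four weekly visits with ads at Visits 1-3 (Protocol, Procedures); 500 per arm, up to 33% dropout, ICC .7, design effect 2.4, d = .25 (SAP, Sample size and power); alpha .05 (SAP, Primary analyses). Assumed: two-sided tests; 670 vs 335 completers (1000 and 500 × .67); total variance 1 at Visit 4; random slope variance s of 0 to .05; all visit-specific arm differences, since the documents give none.

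**1. The plan's own figure.** Design effect = 1 + (m − 1) × .7. With m = 3 it is 2.4, as stated; with m = 4 it is 3.1. So the power section implies three occasions, although susceptibility is measured at four. A line through Visits 1-4 is the natural reading, but it is an inference. The power level for d = .25 is not given.

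**2. Line weights.** With times −3, −2, −1, 0 and compound symmetry:
- slope effect = −.3 D1 − .1 D2 + .1 D3 + .3 D4
- Visit 4 effect = −.2 D1 + .1 D2 + .4 D3 + .7 D4

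**3. Sign.** Let the benefit grow from .10 to .25 SD in steps of .05. For susceptibility (Real Cost minus control): −.3(−.10) − .1(−.15) + .1(−.20) + .3(−.25) = −.05 per week. For an outcome expected to rise, the mirror image is +.05.

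| Indicator | Susceptibility | Risk beliefs |
|---|---|---|
| Real Cost = 1 | −.05, read as diminished (wrong) | +.05, read as increased (right) |
| Control = 1 | +.05, read as increased (right) | −.05, read as diminished (wrong) |

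No single coding works for both columns. This does not depend on the assumed sizes.

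**4. Attribution** (from here, positive = benefit). If D2 = D3 = D4 = D, the slope is −.3 D1 − .1 D + .1 D + .3 D = .3(D − D1). With D = .25:
- D1 = .40 gives −.045 per week
- D1 = .10 gives +.045
- D1 = 0 gives +.075

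The Visits 2-4 slope is zero in all three. Conversely, differences of .30, .15, .20, .25 grow by .05 per week over Visits 2-4, yet the four-visit slope is −.09 − .015 + .02 + .075 = −.01. With D1 = .40 it is −.04, the opposite sign.

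**5. How often the days-vaped slope would be significant.** Visit 1 precedes all exposure, so D1 = 0 in expectation; if the effect is then flat at δ, the slope is .3δ. SE = √[(.3 × .2 + s)(1/670 + 1/335)] = .0164 (s = 0) or .0222 (s = .05).

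| δ | Slope | Significant at .05 | Significant at .05/28 |
|---|---|---|---|
| .25 | .075 | 92% to over 99% | 60-93% |
| .15 | .045 | 53-78% | 14-35% |
| .10 | .030 | 27-45% | 4-10% |

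The last column is the strictest Benjamini-Hochberg step if the family is 14 outcomes × intercept and slope (assumed). At δ = .25 and .05, ICC .5 gives 82-94% and ICC .8 gives 96% to over 99%. The .15 row also applies to a scale measured after the ads at Visit 1 whose Visit 1 difference is .15 away from a flat later effect, since the slope is again ±.045.

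**6. Visit 4 effect.** The bias is −.2 × (departure of D1 from the line through Visits 2-4). For .30, .15, .20, .25 that line reaches .10 at Visit 1, so the departure is .20 and the estimate is .25 − .04 = .21. The factor is −.08 to −.23 under AR(1) correlation of .8, doubled Visit 1 residual variance, or 33% monotone dropout. With no effect at any visit, or a linear effect, there is no bias.

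**The case against.** The strongest reply is that little of this touches the primary inference. The primary hypothesis concerns the 3-week follow-up and is tested on the intercept; the protocol openly describes the timing split; and the SAP gives a direction for every vaping outcome, so a careful reader can recover the meaning of a slope without any p-value changing. That stands, and it limits the point to the slope reading plus a sensitivity check at Visit 4.

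It is also true that the percentages assume real effects of chosen size, and that d = .25 and ICC .7 are planning values that the SAP does not tie to days vaped. The masking patterns are illustrations.

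Several stronger readings are tempting but unsupported:

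- *The slope test has an inflated false-positive rate.* It does not. With no effect at any visit, the expected slope effect is zero. The percentages are the power to detect a real divergence that would then be misattributed.
- *Inconsistent timing affects days vaped.* It does not; days vaped is reported before the ads at every visit. Its problem is onset, because Visit 1 precedes all exposure.
- *A growing benefit on susceptibility always gives a negative slope effect.* Only if Real Cost is coded 1, which the SAP does not say.
- *The SAP definitely fits all four visits.* It lists none. If Visit 1 was meant to be left out, the SAP should say so; the sign problem would remain.
- *Attention and negative affect share the timing fault.* They do not; they are always taken right after the ads.

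**Conclusion.** The slope rule should be changed. The sign part is certain from the documents: outcomes expected to fall and outcomes expected to rise cannot share one raw-scale rule. The attribution part holds if Visit 1 is on the line. The slope then carries immediate-versus-delayed response (susceptibility and similarly timed scales) or onset (days vaped, days smoked), and it can be clearly nonzero without build-up or near zero despite it. How often this would mislead depends wholly on visit-specific effects that the documents do not give.

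A reader might infer that the primary analysis is invalid or that the latent curve model must be replaced. The documents do not support that. The Visit 4 estimate is biased only if the Visit 1 difference is off the later line, and then modestly. The SAP speaks of establishing a linear trajectory, which implies some check of shape, but it states no criterion or fallback. A sensitivity analysis is the proportionate response.

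**What to change.** 1. State the arm coding and orient every outcome so that positive means benefit. For smoking outcomes without a directional hypothesis, define an increase as growth in the absolute arm difference.
2. State which visits enter each model. Except for attention and negative affect, do not read a slope that includes Visit 1 as an effect of repeated viewing; report a Visits 2-4 slope.
3. For all outcomes, including attention and negative affect (whose Visits 1-3 slope stays as planned), say that number of viewings and elapsed time are confounded, because no arm has a single exposure.
4. Add a sensitivity analysis of the Visit 4 effect, using visit-specific arm differences under FIML or a latent curve with the Visit 1 mean freed in both arms, and state the linearity criterion and fallback. Freeing only the arm difference at Visit 1 is not enough: control participants also watch vaping videos before the Visit 1 scales, and if both arms are off the line by c, the Visit 4 effect is biased by .2c and the slope by .3c.
5. For days vaped and days smoked, treat Visit 1 as a pre-exposure baseline.

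**Cost.** This is SAP wording and one added analysis, with no new data. Under the assumed structure:

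- *Visit 4.* Variance goes from .91 to .95 (Visit 1 freed) or 1.0 (visit-specific), so the SE rises 2% or 5%. Power at d = .25 goes from 97.5% to 96.9% or 96.2%.
- *Visits 2-4 slope.* Variance goes from .06 to .15 (s = 0) or .11 to .20 (s = .05), so the SE rises 58% or 35%. A true slope of .05 per week then has only 39-49% power. This is a real loss and should be stated.
- *Days outcomes.* With Visit 1 as baseline, Visit 4 variance is 1 − ICC² / (1 + 9s), compared with ICC + .7(1 − ICC) from the line. The SE changes by −25% to −15% at ICC .7, −6% to −1% at ICC .5, and +7% to +9% at ICC .3 (s from 0 to .05).
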